### 8. PATIENT ACCOUNTING AND DISPOSITION

## 8.1. Patient Disposition

Information for this presentation of the recorded data will come from the **Study Exit** case report form and the **Procedure** form. A complete accounting of patient participation in the study by analysis population will be presented in Table 14.1.1a entitled **Patient Accounting** using the Level 1 table design. The purpose of this table is to provide an accounting of patients from their entrance into the study through the final visit and to account for the evaluations of patients in the analyses of efficacy and safety, including reasons for early study termination. The overall number of patients reported in this table will be based on the number of patients consented and the reasons for screen failure.

Each listing will contain separate flags to indicate if the patient is part of the ITT, FAS and Per-Protocol populations, respectively. Listing 16.1 entitled *Patient Disposition* supports Tables 14.1.1a through 14.1.1.2. This listing will be sorted by site number and patient number. Listing 16.2.1 entitled *Inclusion Criteria* displays the data from the Inclusion Criteria case report form. The data will be displayed for each patient and for each inclusion criterion. Listing 16.2.2 entitled *Exclusion Criteria* displays the data from the Exclusion Criteria case report form. The data will be displayed for each patient and for each exclusion criterion. Listing 16.3.1 entitled *Protocol Deviations* will list all protocol deviations for each patient, and identify if they are major. The deviation code and description, visit and action, will also be included in the listing. The list of what constitutes a major deviation will be finalized prior to database lock.

# 8.2. Patient Demographics Recorded at Baseline

Case Report Form Data Source: Demographics [Date of Birth, Sex, Child-bearing potential, Ethnicity, Race, age, Date of ICF] / Visit: Screening and Baseline

Data will be summarized and reported in Table 14.1.2 entitled *Summary of Patient Demographics* (ITT population) using the Level 1 table design; Table 14.1.2a will be restricted to the ITT population. This table summarizes the patient population with respect to age at entry into the study, sex, weight, height, and BMI. Age will be reported in years. Age, weight (lbs.), height (inches) and BMI will be summarized using descriptive statistics: n, arithmetic mean, standard deviation, median, and range (*i.e.*, minimum and maximum values). Age will also be presented in mutually-exclusive categories: >=65 to <65, years of age. Sex will be summarized using counts and percentages. Patients with missing data that cannot be resolved prior to database lock will not be included in the tabulation and excluded from the summary statistics; all demographic data will be presented in a listing. Sites that do not provide the full date of birth for a patient will not be considered missing data if the day of birth is not provided. Under this scenario, the first day of the month will be used in the calculations.

The supportive data for Tables 14.1.2 and 14.1.2a will be presented in Listing 16.4.1 entitled *Patient Demographics*. This listing will be sorted by site number and patient number and contain a separate flag to indicate if the patient is part of the FAS and Per-Protocol populations, respectively.

Version 1.0 Confidential Page 24 of 42

# 8.3. Medical History Recorded at Baseline

Information for this presentation of the recorded data will come from the **Medical History** case report form. Data will be summarized and reported in Table 14.1.3 entitled *Summary of Patient Medical History* (ITT population) using the Level 1 table design; Table 14.1.3a will be restricted to the FAS population. This table summarizes the patient population with respect to risk factors using counts and percentages. Patients with missing data that cannot be resolved prior to database lock will not be included in the tabulation and excluded from the summary statistics; all risk factor data will be presented in a listing.

The supportive data for Tables 14.1.3 and 14.1.3a will be presented in Listing 16.4.2 entitled *Medical History*. This listing will be sorted by Diabetes Site number, Endoscopy Site number and patient number and contain a separate flag to indicate if the patient is part of the FAS and PP populations, respectively.

# 8.4. Index Procedure and Hospital Admission Details

Information for this presentation of the recorded data will come from the Index **Procedure** case report form. Data will be summarized and reported in Table 14.1.4 entitled *Summary of the Index Procedure and Hospital Admission Details* (ITT population) using the Level 1 table design; Table 14.1.4a will be restricted to the FAS population.

The supportive data for Tables 14.1.4 and 14.1.4a will be presented in Listing 16.4.3 entitled *Index Procedure and Hospital Admission Details*. This listing will be sorted by site number and patient number and contain a separate flag to indicate if the patient is part of the FAS and PP populations, respectively.

# 8.5. Laboratory Tests

Information for this presentation of the recorded data will come from the **Laboratory Tests** case report form. Data will be summarized and reported in Table 14.1.5 entitled *Summary of the Laboratory Tests Recorded Prior to the Procedure* (ITT population) using the Level 1 table design; Table 14.1.5a will be restricted to the FAS population. The following laboratory values will be summarized based on the construct of the variable using the ITT population: continuous, multinomial, or binary.

Each laboratory parameter recorded on a continuous scale will be summarized using descriptive statistics: n, mean, standard deviation, median, minimum and maximum values. Patients with missing data that cannot be resolved prior to database lock will not be included in the tabulation and excluded from the summary statistics.

The supportive data for Tables 14.1.5 and 14.1.5a will be presented in Listing 16.4.4 entitled *Laboratory Tests*. This listing will be sorted by site number and patient number and contain a separate flag to indicate if the patient is part of the FAS and Per-Protocol populations, respectively. Unscheduled laboratory tests entered into the EDC system will also be contained within the listing.

### **8.6.** Unscheduled Visit Information

Information for this presentation of the recorded data will come from the individual datasets where the visit name is listed as *Unscheduled*. Listing 16.4.9 entitled *Unscheduled Visit Information* will be sorted by site number, and patient.

The table below provides the specification for assignment of an unscheduled visit. If there are multiple records within an interval, date of the latest record will be used.

			Protocol Visit Window			Expanded Visit Window		
Visit Name	Clinic (Visit) / (R)emote Visit	Timing of the Visit (weeks)	Protocol Visit Window (days)	First Interval Day	Last Interval Day	First Interval Day	Last Interval Day	Expanded Visit Window (days)
Screening	R1	-12	-84 to -5	-84	-5			
Baseline[1]	V2	-3	-28 to -1	-28	-1			
Index Procedure	V3	0						
Week 1	R4	1	±2	5	9	5	9	2
Week 2	R5	2	±3	11	17	10	18	4
Week 4	V6	4	±5	23	33	19	37	9
Week 8	R7	8	±7	49	63	38	74	18
Week 12	R8	12	±7	77	91	73	95	11
Week 16	R9	16	±7	105	119	96	128	16
Week 20	R10	20	±7	133	147	129	151	11
Week 24	V11	24	±7	161	175	152	184	16
Week 28	R12	28	±7	189	203	185	207	11
Week 32	R13	32	±7	217	231	208	240	16
Week 36	V14	36	±7	245	259	241	263	11
Week 40	R15	40	±17	273	287	264	296	16
Week 44	R16	44	±7	301	315	295	321	13
Week 48 (End of Study )	V17	48	30	306	366	322	366	14

Visit Name	Clinic (Visit) / (R)emote Visit	Timing of the Visit (weeks)	Target Visit Day	Number of Days on Either Side of the Target Day to define the Expanded Time Window
Screening	R1	-12		
Baseline[1]	V2	-3		
Index Procedure	V3	0		
Week 1	R4	1	7	2
Week 2	R5	2	14	4
Week 4	V6	4	28	9
Week 8	R7	8	56	18
Week 12	R8	12	84	11
Week 16	R9	16	112	16
Week 20	R10	20	140	11
Week 24	V11	24	168	16
Week 28	R12	28	196	11
Week 32	R13	32	224	16
Week 36	V14	36	252	11
Week 40	R15	40	280	16
Week 44	R16	44	308	13
Week 48 (End of Study )	V17	48	336	14

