7.13.1 Screening Visit – Visit 1 (within 84 days from the Index Procedure)

To limit in-person visit, the screening visit may be performed remotely. Screening BMI eligibility will be based on self-reported height and weight. Potentially eligible participants will be scheduled for laboratory tests at the study laboratory. The following procedures/assessments will be performed during this visit:

- Informed consent prior to the conduct of any study-related procedures
- Inclusion and exclusion criteria
- Demographics
- Medical history including diseases, disorders and medications
- Diabetes history including diabetes medications
- Laboratory tests:
 - o Hematology (CBC with differentials)
 - Metabolic panel (liver and renal function)
 - o Fasting serum C-peptide, FPG, HbA1C

- GAD antibodies
- o TSH
- H. Pylori (breath or stool test)
- Pregnancy test for females capable of becoming pregnant
- Registration on screening log

Once all data including testing results related to the screening have been obtained, the investigator will review the participant's eligibility for the study. If deemed eligible, participant will be scheduled for the baseline visit.

Eligible participant must meet all the inclusion criteria and none of the exclusion criteria with one exception. If a participant has met all other criteria except that s/he has been on stable glucose-lowering medication(s) for less than 12 weeks at the time of screening visit, the participant can be scheduled for baseline visit such that s/he will be on stable medication for 12 weeks at the time of baseline visit.

It is recognized that COVID-19 restrictions may cause delays in scheduling the index procedure, resulting in the screening visit being out of window. In case the screening visit is out of the visit window, the investigator will reassess the participant's eligibility by evaluating any changes in the participant's medical history and medications. The investigator may decide to repeat certain screening tests based on his/her medical judgement. If the investigator determines that the participant remains eligible for participating in the study, the participant may proceed to Baseline visit. Investigator's assessment and any repeated test results will be documented on eCRFs.

7.13.2 Baseline Visit – Visit 2 (within 21 days prior to the Index Procedure)

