APPENDIX 2. SCHEDULE OF ACTIVITIES

	b o	П	Ire	_	2	4	æ	12	91	02	24	87	32	36	0#	4	48 tudy	e uafi 24	ire atio
	Screening	Baseline ^{III}	Index Procedure	Week 1	Week 2	Week 4	Week 8	Week 12	Week 16	Week 20	Week 24	Week 28	Week 32	Week 36	Week 40	Week 44	Week 48 End of Study	Premature discontinuati on within 24 weeks	Pre-mature discontinuatio n post 24
Clinic Visit(V)/Remote Visit (R)	R1	V2	V3	V/R4	R5	V/R6	R7	V/R8	R9	R10	V11	R12	R13	V/R14	R15	R16	V17	V17A	R17A
Timing of visit (weeks)	-12	-3	0	1	2	4	8	12	16	20	24	28	32	36	40	44	48		
Visit window (days)	-84 to -5	-21 to -1	-	±2	±3	±5	±7	±7	±7	±7	±7	±7	±7	±7	±7	±7	+30		
SUBJECT RELATED INFO/ASSESMENTS																			
Informed consent	X																		
In/exclusion criteria	X	X																	
Medical history/Diabetes history	X			2															
Concomitant medication	X	X	X	X		X		X			X			X			X	X	X
Demographics	X																		
Treating physician diabetes assessment and medication review		X	X	Х	X	X	X	X	X	X	X	X	X	X	X	Х	X	X	
Lifestyle Counseling		X		X	X	X	X	X	X	X	X	X	X	X	X	X	X	X	
Diabetes education, Handout and instruct in CGM use		X																	
Handout ID card		-	X	2		Al sc			3				8			2			
Study Exit																	X	X	X
VITAL SIGNS AND PHYSICAL EXAMINATION																			
Height		X		2					3				8			2		2	
Body weight		X		X		X		X			X			X			X	X	
BMI		X		X		X		X			X			X			X	X	
Waist circumference		X		2				X			X			X			X	X	
Blood pressure and pulse rate		X	X	X		X		X			X			X			X	X	
Physical examination		Х															X	X	
LABORATORY TESTINGS																			
Fasting plasma glucose	Х	Х				X		X ^[6]			X			X			X ^[6]	Х	
HbA1c	X	Х				X		X			X			X			X	X	
Fasting insulin		X				X		X ^[6]		\vdash	X			X			X ^[6]	X	
Fasting serum C-peptide	X			2		al co			3				8						

	Screening	Baseline ^[1]	Index	Week 1	Week 2	Week 4	Week 8	Week 12	Week 16	Week 20	Week 24	Week 28	Week 32	Week 36	Week 40	Week 44	Week 48 End of Study	Premature discontinuati on within 24 weeks	Pre-mature discontinuatio n post 24
Clinic Visit(V)/Remote Visit (R)	R1	V2	V3	V/R4	R5	V/R6	R7	V/R8	R9	R10	V11	R12	R13	V/R14	R15	R16	V17	V17A	R17A
Timing of visit (weeks)	-12	-3	0	1	2	4	8	12	16	20	24	28	32	36	40	44	48		
Visit window (days)	-84 to -5	-21 to -1	-	±2	±3	±5	±7	±7	±7	±7	±7	±7	±7	±7	±7	±7	+30	37	
MMTT (Mixed meal tolerance test)		X	_	5				X	3								X	X	
HOMA-IR		X				X		X			X			X			X	X	
Fasting lipid panel		X		2							X						X	X	
Metabolic Panel [2]	X	X		X				X			X			X			X	X	
Pancreatic Enzyme (Lipase, Amylase)		X		X				X											

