The Level 3 display will be used for summarizing the parameters recorded multiple times during the follow-up visits. An example of the layout is presented below; rows will be repeated for all visits where a measurement is recorded using the expanded time windows.

Version 1.0 Confidential Page 18 of 42

Level 3a Display

			ou Dispiuj		
Parameter and Statistic	Observation Time	Device Generation 1 / 600 Volts / Single Treatment	Device Generation 1 / 600 Volts / Double Treatment	Device Generation 2 / 750 Volts / Double Treatment	All Patients
HbA1c	Baseline				
HbA1c	Post-Procedure Visit xxx				
HbA1c	Change from Baseline				

Level 3b Display

Parameter and Statistic	Observation Time	Device Generation 1 / 600 Volts / Single Treatment	Device Generation 1 / 600 Volts / Double Treatment and Device Generation 2 / 750 Volts / Double Treatment	All Patients
HbA1c	Baseline			
HbA1c	Post-Procedure Visit xxx			
HbA1c	Change from Baseline			

There will be 2 sets of comparative analyses prepared, each predicated on different combinations of device generation, voltage, and single vs. double treatment. The planned comparisons are outlined below.

### Comparison Set 1

Device Generation 1 / 600 Volts / Single Treatment vs.

Device Generation 1 / 600 Volts / Double Treatment vs.

Device Generation 2 / 750 Volts / Double Treatment

#### Comparison Set 2

Device Generation 1 / 600 Volts / Single Treatment vs.

Device Generation 1 / 600 Volts / Double Treatment plus Device Generation 2 / 750 Volts / Double Treatment

Supportive individual patient data Listings will be sorted and presented by site number, patient number and visit date, if applicable. Listings will also include the number of days relative to the DMR index procedure. Specific algorithms are discussed for imputing missing or partially missing data, if deemed appropriate, under specific data topics. Imputed or derived data will be flagged in the individual patient data Listings. Imputed data, restricted to dates, will not be incorporated into any raw or primary datasets from the electronic capture system. The imputed data will be retained in the derived / analysis datasets.

Summary statistics will consist of the number and percentage of responses or counts at each level for categorical variables (e.g. race). For continuous variables, and the sample size (n), mean, median, standard deviation (SD), minimum, and maximum values will be presented.

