### **Ninth Secondary Endpoint**

The distribution of this endpoint is binary. Proportion of treated patients who achieve a HbA1c improvement of  $\geq 0.5\%$  or more at 24 weeks from baseline and maintained at 48 weeks. Patients who fail to maintain HbA1c improvement  $\geq 0.3\%$  at 48 weeks, for any reason, will be counted as not having achieved this endpoint. Patients who fail to achieve a HbA1c  $\geq 0.5\%$  at 24 weeks will be excluded from the tabulation. The primary population for analysis of this endpoint will be the FAS population.

Proportion of treated patients with an HbA1c improvement  $\geq 0.5\%$  from baseline at 24 weeks maintained at 48 weeks.

**Tenth Secondary Endpoint:** The distribution of this endpoint is continuous. The primary population for analysis of this endpoint will be the FAS population. Change in weight from baseline (post-baseline minus baseline) by visit. Weight change will be reported in both kilograms and %TBWL.

**Eleventh Secondary Endpoint:** Change in glucose-lowering medication usage.

**Twelfth Secondary Endpoint:** The distribution of this endpoint is continuous. The primary population for analysis of this endpoint will be the FAS population. Change in liver enzyme from baseline at 24 weeks (post-baseline minus baseline) for Alanine Aminotransferase (ALT).

**Thirteenth Secondary Endpoint:** The distribution of this endpoint is continuous. The primary population for analysis of this endpoint will be the FAS population. Change in liver enzyme from baseline at 24 weeks (post-baseline minus baseline) for Aspartate Aminotransferase (AST).

Version 1.0 Confidential Page 31 of 42

**Fourteenth Secondary Endpoint:** The distribution of this endpoint is continuous. The primary population for analysis of this endpoint will be the FAS population. Change from baseline in blood pressure by visit (systolic and diastolic run separately).

**Fifteenth Secondary Endpoint:** The distribution of this endpoint is continuous. The primary population for analysis of this endpoint will be the FAS population. Change in lipid profile from baseline by visit: total cholesterol

**Sixteenth Secondary Endpoint:** The distribution of this endpoint is continuous. The primary population for analysis of this endpoint will be the FAS population. Change in lipid profile from baseline by visit: triglycerides

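### The two visit-window tables in SAP 8.6 disagree with each other and with the protocol, and the SAP does not say which limits govern Week 48

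*SAP*

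**What the plan says.** SAP 8.6 (Unscheduled Visit Information) opens its specification with "The table below provides the specification for assignment of an unscheduled visit". The first table gives, for each visit, a protocol window and an expanded window, each with a first and last day, plus a width for the expanded window. The second gives only a target day and a half-width, under the column title "Number of Days on Either Side of the Target Day to define the Expanded Time Window".

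For Week 48 the first table reads "Week 48 (End of Study ) V17 48 30 306 366 322 366 14": protocol interval 306-366, expanded interval 322-366, width 14. The second reads "Week 48 (End of Study ) V17 48 336 14": target day 336 with 14 days either side.

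The visit-window row of the Schedule of Activities (Protocol Appendix 2) gives +30 for Week 48, ±7 for Weeks 40 and 44, and -21 to -1 for baseline. The heading of Protocol 7.13.2 agrees on baseline: "within 21 days prior to the Index Procedure". The SAP table has -28 to -1, although SAP 5.1 itself repeats the 21-day limit.

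The windows reach beyond unscheduled visits. SAP 7 says of the Level 3 by-visit displays that "rows will be repeated for all visits where a measurement is recorded using the expanded time windows". SAP 7.3.1 bars imputation of anything but dates. For the ninth secondary endpoint (HbA1c improvement at Week 24 maintained at Week 48), SAP 9 says that a Week 24 responder who does not maintain improvement, "for any reason, will be counted as not having achieved this endpoint". Week 24 non-responders are left out of the tabulation.

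**The concern.** A visit-window table has to give each measurement one visit. This one gives two answers for Week 48, and it gives two visits for some days.

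Week 48 is where this costs most. Per the Schedule of Activities it is one of only two scheduled post-procedure MMTT visits (Weeks 12 and 48) and one of two lipid visits (Weeks 24 and 48). It is also the final HbA1c. A programmer who applies the half-width of 14, which both tables print, would discard values from visits made on time under the protocol. A programmer who applies the printed limits 322-366 would keep them. Nothing in the SAP says which is right, so the choice could be made with the data in hand.

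**Working it through.** **Inputs.** SAP 8.6, both tables; Protocol Appendix 2; SAP 7 for day numbering. Target day = 7 × week, so Week 48 is day 336.

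**1. Reproducing the expanded intervals.** Interval = target day ± half-width. This reproduces 13 of the 14 post-procedure rows of the first table. For example, Week 24 is 168 ± 16 = 152-184, as printed. The exception is Week 48: 336 ± 14 = 322-350, against 322-366 printed.

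**2. SAP protocol columns against the protocol.**

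| Visit | SAP entry | SAP limits | Protocol |
|---|---|---|---|
| Baseline | -28 to -1 | -28 to -1 | -21 to -1 |
| Week 40 | ±17 | 273-287 | ±7 = 273-287 |
| Week 48 | 30 | 306-366 | +30 = 336-366 |

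The other 12 post-procedure rows agree. The Week 48 entry treats a one-sided allowance as two-sided (336 - 30 = 306). It therefore shares days 306-315, ten days, with the SAP's own Week 44 interval of 301-315. The protocol's own windows do not overlap.

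**3. Days in two expanded windows** (the same in both tables).
- Week 8 is 38-74 and Week 12 is 73-95: days 73 and 74 are shared.
- Week 40 is 264-296 and Week 44 is 295-321: days 295 and 296 are shared.
- No other pair overlaps. The SAP's tie rule takes the latest of several records in one interval; it does not cover one record in two intervals.

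**4. Permitted Week 48 days with no window.** Permitted days: 366 - 336 + 1 = 31.

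| Governing table | Procedure = Day 0 | Procedure = Study Day 1 |
|---|---|---|
| First (322-366) | 0 of 31 | 1 of 31 |
| Second (322-350) | 366 - 350 = 16 of 31 (52%) | 17 of 31 |

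The right-hand column matters because SAP 7 calls the procedure day Relative Study Day 1, whereas targets of 7 × week fit a count from Day 0. Under Study Day 1 numbering the last permitted Week 48 day becomes day 367, outside even the first table.

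**5. Possible effect on the ninth endpoint.** One maintained responder wrongly counted as a failure lowers the proportion by 100/R points, where R is the number of Week 24 responders. R is not given in the documents; assumed range 5 to 20.

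| R | Change in points |
|---|---|
| 5 | 20.0 |
| 10 | 10.0 |
| 15 | 6.7 |
| 20 | 5.0 |

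With 20 patients planned, the change cannot be smaller than 5 points.

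**The case against.** The strongest reply is that SAP 8.6 concerns unscheduled visits. Week 48 is a scheduled visit, and nothing in 8.6 says that a scheduled visit is reassigned or dropped by these tables. This stands in part. SAP 7 does carry the expanded windows into the Level 3 displays, so by-visit results are exposed.

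A reader might infer more: that late but compliant Week 48 visits will be scored as failures on the ninth endpoint. The documents do not support that. SAP 9.2 classes this endpoint as binary at a single time point and reports it in Level 1 tables, and no text says that the windows feed it. The top-line table list includes a by-visit summary of HbA1c improvement, which makes the link plausible but does not state it. The result also needs the second table to govern. Even then, only a responder who truly maintained improvement would be misclassified; one who lost response is a failure either way.

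A reader might also take 52% as a share of visits. It is a share of permitted days. The documents give no distribution of visit dates.

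Several of the other discrepancies have little effect:
- The four shared days lie outside every protocol-compliant interval. Weeks 8, 40 and 44 have no scheduled HbA1c, FPG, weight or blood pressure, so CGM and off-window or unscheduled records are mainly affected.
- The 306-315 overlap is in the protocol columns, not the expanded ones.
- SAP 7 takes baseline as the values recorded immediately before the procedure, so the -28 entry changes no stated calculation.
- The Week 40 limits are right; only the label is wrong.

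**Conclusion.** The table contradictions are exact and should be corrected before analysis. The one with a real consequence is Week 48. If the ±14 rule governs and windows apply to scheduled visits, 16 of 31 permitted days have no visit, and HbA1c, MMTT and lipid values from those days are lost to the by-visit results without imputation. If the printed limits 322-366 govern and days count from Day 0, nothing is lost.

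An effect on the ninth endpoint needs a further assumption that the SAP does not state, namely that the same windows feed it. On that assumption, each maintained responder seen on days 351-366 would lower the proportion by at least 5 points, or 20 points with 5 responders.

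The remaining items are consistency corrections. The primary safety endpoint is tabulated by event date and does not use visit windows. All testing is declared informative only (SAP 7.1). The matter is therefore one of a reproducible analysis rule, not of the trial's main conclusion.

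**What to change.** Keep one table and delete the second, together with the half-width column, which cannot describe asymmetric windows.

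- **Expanded windows:** Week 8, 38-72; Week 12, 73-95; Week 40, 264-294; Week 44, 295-321; Week 48, 322-366. The other rows stay. These limits meet without gaps or overlaps and contain every protocol-compliant day of their visits.
- **Protocol columns:** baseline -21 to -1; Week 40 ±7; Week 48 336-366.
- **Day convention:** state that the limits are days since the procedure (procedure = Day 0) and reconcile this with Relative Study Day 1 in SAP 7, or shift every post-procedure limit by one day. Leave the primary endpoint's day-84 cut-off unchanged.
- **Governing rule:** state whether the nominal visit label or the window decides for scheduled visits, and which of the two feeds the Week 24 and Week 48 binary HbA1c endpoints.

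The cost is a correction to one SAP table and a few sentences, with no change to visits, data collection or trial conduct.

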6.2.1 Background Glucose-Lowering Medications

Eligible participants must be on two to three non-insulin glucose-lowering medication(s), one at maximum tolerated dose and another at half-maximum dose at least, without a severe hypoglycemic event within the past six months of the screening visit.

Participant's background medication will be kept stable (no change in medication or dose) for at least 12 weeks prior to the Baseline Visit.

Peri-procedurally, the dose of medications with hypoglycemic risks will be adjusted per guidelines provided in **Section 6.2.2**.

Following the transitional diet period, participant's medication will be titrated to the background level and maintained stable until the Week 24 Visit has been completed. Medication and/or dose change necessary for managing hypoglycemia, hyperglycemia, or other safety concerns is permitted. Reason for the medication change must be documented on eCRF.

Following the Week 24 Visit, participants will be managed according to the current (2021) guidelines of the American Diabetes Association² and their glucose-lowering medications will be optimized as necessary to reach an HbA1c target of 7%.

Background medications are non-investigational products. They should be used in accordance with standard of care and their approved labeling. They will not be provided by the sponsor.

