6.2.3 Guidelines for Managing Hyperglycemia

After the background medications have been titrated back to baseline level following the transitional diet period, participants with severe, persistent hyperglycemia should be offered treatment intensification.

In the event of suspected persistent hyperglycemia in a subject based on either symptoms of hyperglycemia (eg, thirst, polyuria, blurred vision), CGM readings of >250 mg/dL for > 30% of the time, or repeated fasting CGM readings above 270 mg/dL (e.g. occurring 3 days in a week), the investigator should perform additional laboratory tests to assess whether rescue therapy is warranted.

Participants meeting the following criteria should be offered rescue medication (i.e. intensification of glucose-lowering background medication and/or initiation of basal insulin).

- FPG > 270 mg/dL, confirmed by repeated measures more than 3 days apart, and no intercurrent cause can be identified, or
- HbA1c is >8.0% AND the interval improvement is <0.5% from baseline, by Week 12

After Week 24, participants should be offered treatment intensification if they do not reach their HbA1c target, which for most individuals is 7.0%.

The above criteria and medications are provided as a guideline. Investigators should always exercise his/her clinical judgement based on individual conditions to protect participant's safety and wellbeing.

Participants who meet rescue criteria before Week 24 should first complete the Week 24 visit activities within 5 days before initiation of the rescue medication to ensure that important trial endpoint measurements are collected and be provided the rescue therapy.

Medication changes and reasons for the changes will be documented on the eCRFs. Medications used to manage hyperglycemia are non-investigational and will not be provided by the sponsor.

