# 7.3. Handling of Missing Data

# 7.3.1. Missing and Censored Data

All tabulations and analyses will be based on the observed data without imputation, with the exception of dates.

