### **Eighth Secondary Endpoint**

The distribution of this endpoint is binary. The analysis will be based on the proportion of patients that meet the endpoint at 24 weeks post-procedure. The primary population for analysis of this endpoint will be the FAS population.

Proportion of treated patients with an HbA1c improvement of  $\geq 0.5\%$  from baseline at 24 weeks (24 week score minus baseline score). Patients who fail to have HbA1c improvement of  $\geq 0.5$  points from baseline, for any reason, will be counted as not having achieved this endpoint.

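### The SAP drops the protocol's rescue provisions, so a post-rescue HbA1c can stand as the principal Week 24 result in the FAS

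*SAP*

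**What the plan says.** **Protocol.** Under section 6.2.3, participants who meet rescue criteria before Week 24 "should first complete the Week 24 visit activities within 5 days before initiation of the rescue medication"; the stated purpose is to secure the endpoint measurements. One criterion, applied by Week 12, is HbA1c above 8.0% with an improvement from baseline of less than 0.5%. Section 12.4.1 generally leaves missing data unimputed, but makes an exception: effectiveness values after rescue for hyperglycemia are replaced by the last value before it. Section 6.2.1 opens medication optimisation after the Week 24 visit: "Following the Week 24 Visit, participants will be managed according to the current (2021) guidelines".

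**SAP.** Section 7.3.1 has no rescue exception: "All tabulations and analyses will be based on the observed data without imputation, with the exception of dates". Section 8.6 introduces its window table with "The table below provides the specification for assignment of an unscheduled visit", gives Week 24 a target of day 168 and an expanded window of days 152-184, and settles multiple records with "If there are multiple records within an interval, date of the latest record will be used". Section 7 extends the windows to the Level 3 by-visit displays, for which HbA1c is the example: "rows will be repeated for all visits where a measurement is recorded using the expanded time windows". Section 4.2.1 makes Week 24 the principal time point for HbA1c. Section 6 makes the FAS the primary effectiveness population.

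**The concern.** The protocol measures Week 24 HbA1c on background medication so that the change can be read as the effect of the procedure. Nothing in the SAP gives effect to that. It does not say where a brought-forward Week 24 assessment belongs, and it does not set aside values taken after rescue.

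The overlap with the responder endpoint makes this sharper. A participant rescued on the HbA1c criterion has, by definition, improved by less than 0.5, which is the threshold of the eighth secondary endpoint. Under the protocol's rule that participant is a non-responder at Week 24, provided the brought-forward assessment confirms the qualifying value. Under the SAP the same participant can become a responder because of the rescue drug. The mixed-model estimate at Week 24 is exposed in the same way.

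**Working it through.** **Inputs.** Targets, half-widths and interval days come from SAP 8.6, and days are counted as in that table. HbA1c analysis visits are Weeks 4, 12, 24, 36 and 48 (SAP 9, third secondary endpoint). Group sizes of 3, 7 and 10, total 20, come from SAP 3.

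**The plan's own figure.** Expanded window = target ± half-width, under the column headed "Number of Days on Either Side of the Target Day to define the Expanded Time Window".
- Week 24: 168 ± 16 = days 152-184, as printed. The protocol window is 168 ± 7 = days 161-175.
- 13 of the 14 post-procedure rows reproduce. Week 48 does not: 336 ± 14 = 322-350, but the table prints 322-366. This does not affect Week 24.

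**Route 1: rescue near Week 12, then the ordinary Week 24 visit.** Take the brought-forward assessment on days 77-91 (the Week 12 protocol window), with rescue starting within 5 days, so on days 77-96. The ordinary Week 24 visit on days 161-175 then follows between 161 − 96 = 65 and 175 − 77 = 98 days of rescue. If the early assessment is slotted by date, the post-rescue value is the only record in days 152-184. SAP 7.3.1 keeps it; protocol 12.4.1 would replace it. The latest-record rule plays no part here.

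If the early assessment keeps its Week 24 label, there are two Week 24 records, and the SAP's only tie-break is the latest.

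**Route 2: brought-forward assessment slotted by date.**

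| Day of assessment | SAP window | Number of days | HbA1c analysis visit? |
|---|---|---|---|
| 77-95 | Week 12 | 19 | Yes, but the wrong one |
| 96-128 | Week 16 | 33 | No |
| 129-151 | Week 20 | 23 | No |
| 152-160 | Week 24 | 9 | Yes |

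Of the 84 days from 77 to 160, 19 + 33 + 23 = 75 fall outside the Week 24 window. This counts days; it is not a probability. Displacement of the scheduled Week 12 value matters little, because both values precede rescue and lie days apart.

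**Route 3: brought-forward assessment on days 152-160.** A later visit on days 161-175 is in the same window, so the latest record, now post-rescue, supersedes it. The two are 161 − 160 = 1 to 175 − 152 = 23 days apart, which limits the drug effect.

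**Route 4: intensification after the Week 24 visit.** After a visit on day 161, 168 or 175 the window stays open 184 − 161 = 23, 184 − 168 = 16 or 184 − 175 = 9 days. No HbA1c is scheduled between Weeks 24 and 36, so this route needs an unscheduled test.

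**Effect of one reclassified responder** (if all treated participants are in the FAS): 1/20 = 5 points, 1/10 = 10 points, 1/7 = 14.3 points, 1/3 = 33.3 points.

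**Share meeting the Week 12 HbA1c criterion.** The documents give no such figure. Assumptions: baseline HbA1c normal with mean 8.6 and SD 0.7, truncated to 7.5-10.0; change normal and independent of baseline. The quantity is P(baseline + change > 8.0 and change > −0.5).

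| Mean change | SD 0.6 | SD 0.9 | SD 1.2 |
|---|---|---|---|
| −0.3 | 52.5% | 51.5% | 51.1% |
| −0.5 | 40.4% | 43.0% | 44.6% |
| −0.9 | 19.3% | 27.3% | 32.2% |
| −1.2 | 9.0% | 17.7% | 24.0% |

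The range is about 9-53%, or 0.09 × 20 = 1.8 to 0.53 × 20 = 10.6 of 20 participants. Mean changes of −0.9 and −1.2 match the reductions at about six months that protocol section 1.2 reports for hydrothermal resurfacing. The smaller changes and all the SDs are assumptions.

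**The case against.** The best counter-argument is scope. SAP 8.6 is headed and worded for unscheduled visits. A brought-forward visit at which Week 24 activities are done may well be recorded as Week 24 and never re-slotted. The sentence in section 7 does not say that labelled visits are re-slotted by date, or that the mixed model and responder endpoints use the windows. The tie-break also speaks of a date, without saying that the value follows. All of this stands: Routes 2 and 3 are conditional, and a reader who infers that the SAP necessarily misplaces the early assessment goes beyond the text. It does not dispose of Route 1, which rests on section 7.3.1.

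The PP and CC populations require stable medication for 24 weeks, so they exclude participants rescued before then. That stands too, but the FAS, which carries the primary effectiveness analysis, keeps them.

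Some further inferences are tempting but unsupported:
- That 9-53% of participants would have a displaced assessment. The figure counts those meeting a criterion. Rescue is offered as a guideline subject to clinical judgement, and displacement also depends on how visits are recorded.
- That the wide window by itself brings in optimised medication. Optimisation follows the Week 24 visit, not day 175, so a late visit still precedes it.
- That the responder endpoint has a reversed sign. The parenthesis "24 week score minus baseline score" follows the SAP's general change convention, and an HbA1c improvement is plainly a fall.
- That missing Week 24 values are unaddressed in the responder endpoints. The eighth and ninth endpoints already count failure for any reason as non-response.

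**Conclusion.** The concern holds in this form: the SAP omits both of the protocol's rescue provisions and, applied as written, lets a post-rescue HbA1c enter the principal Week 24 result in the FAS. The main cause is the loss of the protocol 12.4.1 replacement; the window table and latest-record rule add to it if records are slotted by date. Route 1 assumes that a rescued participant still attends the ordinary Week 24 visit. The Schedule of Activities lists that visit without an exemption, but the protocol does not say explicitly what follows a brought-forward assessment.

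A post-rescue value tends to flatter the device. The direction is not uniform, however: an empty Week 24 slot counts as non-response in the eighth endpoint.

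Each reclassified responder is worth 5 points overall or 10 points in a group of 10. The number of participants affected cannot be read from the documents; 9-53% is an assumption-based upper bound for displacement through the Week 12 HbA1c criterion. These are secondary endpoints in a 20-participant feasibility study without formal hypothesis tests, so the change should be made but does not threaten the primary safety result.

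**What to change.** 1. State in the SAP that the assessment done before rescue under protocol 6.2.3 is the Week 24 record, by visit label, whatever day it falls on.
2. Replace the latest-record tie-break with the record closest to the target day among those taken before any rescue or post-Week-24 intensification, and say that the value as well as the date is taken from it.
3. Reconcile SAP 7.3.1 with protocol 12.4.1 by restoring the replacement of post-rescue effectiveness values with the last pre-rescue value. Apply the same rule to the by-visit tables, the mixed model and the eighth and ninth endpoints.

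The cost is SAP wording and a derivation flag. Medication changes and their reasons are already documented on the eCRF, so no new data are needed.
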